NOTE: Follow-up assessments will be conducted after 6 months post-intervention. They will occur in November 2012 for the Spring group and in February 2013 for the Summer group.

INCLUSION/EXCLUSION CRITERIA

All individuals invited to participate in the study will be parents of children with developmental delays and clinically significant behavior problems. When there are two parents in the family, both parents will be invited to participate in the study; however, two parents from the same family will only count as one family. In other words, we plan to recruit the parent(s) of 90 children with developmental delays. Criteria for study entry are: (1) Having a child ages 3 to 5, (2) child has been determined by Regional Center (or by an independent assessment) to have a developmental delay, (3) parent(s) report more than 10 child behavior problems (the recommended cutoff score for screening children for treatment of conduct problems) on the Eyberg Child Behavior Inventory (ECBI; Robinson, Eyberg, & Ross, 1980), (4) the parent(s) is not receiving any form of psychological or behavioral treatment at the time of referral (e.g. counseling, parent training, parent support group, etc.), (5) parent(s) agree(s) to participate in the intervention (this requirement will be determined based on whether the parent(s) signs the consent form), and (6) parent(s) must speak and understand English.

Exclusion criteria include parents of children with debilitating physical disabilities or severe intellectual impairments that prevent them from participating in the assessment tasks described in the protocol (e.g. child is not ambulatory). As mentioned above, the child is only involved in the assessment aspects of the study pre-intervention, post-intervention, and at follow-up. During these assessments the child is instructed to play on the floor with the parent for 25 minutes. This task requires the child to understand the researcher's directions, sit-up on his/her own, explore different toys in the room, and interact with the parent. Therefore, if the child has a physical disability or severe intellectual impairment that prevents him or her from participating in the play task the family will be excluded from the study.

Robinson, E. A., Eyberg, S. M., & Ross, A. W. (1980). The standardization of an inventory of child conduct problem behaviors. *Journal of Clinical Child Psychology*, 9, 22-29.

SUBJECT RECRUITMENT & SCREENING

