Institutional Review Board
Approved *[name]*
Date *12/14/17*

RECEIVED

JUL 03 2018

LLUH Responsible
Research Services

Institutional Review Board CHANGE REQUEST FORM

RESEARCH PROTECTION PROGRAMS | LOMA LINDA UNIVERSITY | Office of Research Affairs
[name] [contact] (voice) / [contact] (fax)/e-mail: [contact]

Principal Investigator: [name]

Department: Psychology

Protocol Title: Mindful awareness for parenting stress (MAPS) project for parents of children with developmental delays

IRB #: 5110264

Approval End Date: Aug 20, 2018

Current Stipulations: N/A

I. This Change Request is a result of: (check all that apply)

- Initiated by Sponsor.
- Initiated by local (LLU) Investigator.
- Result of Adverse Event;
re: AE report submitted: ("Unique Identifier")
- Protocol change was necessary to eliminate apparent immediate hazards to subject(s).

II. Protocol Change(s):

- a. Briefly summarize this Change Report, using the preferred wording to appear in the IRB's approval letter.
(This is also the only description appearing in future protocol profiles.)

We are submitting changes to our phone screen, consent form, and questionnaire measures to be consistent with our recently awarded NIH grant (LLeRA 2170159) which falls under this IRB. More specifically, for the phone screen, we are going to ask parents whether their child has an autism spectrum diagnosis, administer the Parenting Stress Index-Short Form 4th Edition instead of the Perceived Stress Scale during the phone screen, and screen for exclusionary criteria. A very similar phone screen was approved for another study of mine (HS 5170325) and these questions have worked very well.

With regard to the consent form changes, we have updated the our previous consent form from the MAPS project to reflect the revised aims and procedures for the NIH grant. We have included a clean copy of our new consent form (title is Stress-reduction techniques for effective parenting skills (STEPS) project), our previous MAPS consent with the track changes, as well as a clean copy of the approved MAPS consent form in order to make the changes clear.

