With regard to questionnaires, for the NIH grant we have added a few parent questionnaires. More specifically, we have included a revised version of the Parenting Stress Index (we are now using the 4th edition instead of the 3rd edition that we used on MAPS), the Social Communication Questionnaire, Attachment Q-Sort questionnaire, Beck Anxiety Inventory, Behavioral Inhibition Questionnaire, Preschool Anxiety Questionnaire, Repetitive Behavior Scale-Revised, Family Resource Scale, Parenting Scale, and Parental Flooding Scale. We have also added one teacher-report questionnaire, the Preschool Anxiety Questionnaire-teacher report version. All of these measures are psychometrically sound and have been frequently used with families of young children with developmental delays and Autism Spectrum Disorder.

b. Classification of significant change(s):

- SAFETY

1a. List any change(s) in monitoring (number each change):

1b. If any item(s) listed above DECREASE monitoring, explain why subject safety will NOT be adversely affected.

- PROCEDURES

2a. List any change(s) in subject-related intervention (number each change): None
2b. What is the scientific justification for item(s) above, and explain how risk to subjects is affected:

There is no additional risk to subjects. The changes are scientifically justified because the revised changes to the phone screen, consent, and questionnaires will more accurately identify the families eligible for this study (phone screen), provide more accurate information to participants about what the study will entail (consent), add additional psychometrically sound measures to assess the constructs of interest, and is in line with the NIH funded proposal.

SUBJECTS

3a. List any change(s) that remove exclusion criteria or broaden inclusion criteria (number each change): The study will now focus on children with Autism Spectrum Disorder specifically, rather than children with developmental delays more broadly.

3b. Justify any item(s) above that remove safety exclusion or modifies fairness in subject selection: This is what was approved by NIH for this project.

ADMINISTRATIVE

4a. Change study title of IRB approval to the following: Stress-reduction techniques for effective parenting skills (STEPS) project

4b. If study personnel will be changed, use the "Request to Change IRB Study Personnel" form.

4c. If sponsor has changed, name of sponsor is:

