*****MAKE SURE TO GET PC MIDDLE NAME**

Because suicidality will be screened for later in the call, you need to get the parent's current location. Ask the parent, "Where are you now?" and try to obtain a physical address.

Make sure to get 2 phone numbers whenever possible (even if one is a relative).

5. Guidelines for section III:

When asking about diagnosis and details, be sensitive to the parent's educational level as well as comfort level.

If they don't seem to understand some of the terminology (e.g. diagnosis), use the suggested alternatives to phrase the questions.

6. Guidelines for section IV:

Ask the parent the PSI-4 Short Form questions provided on the phone screen. As you go thru the questions, make sure to enter answers on the Excel sheet to get a total score. As you type in responses, make sure to use the right scale by checking the scoring keys on the right. If the parent does not reach the clinical cut off (score of 110), they will not be eligible for the study.

If eligible: ***Continue on to Section V***

If not eligible: "Unfortunately, for this study we are only including families with a certain level of parenting stress. Based on your responses, you do not meet criteria at this time. We will have more parenting groups coming up that you may still be eligible for. Would you like to be added to that waitlist?"

If yes: Add to waitlist, make sure to collect all the information that you have not already gotten in this screen

If no: Thank them for their time and for reaching out.

Parents may be sensitive in discussing their stress levels. If necessary, reassure them that you ask the same questions of every parent and that many of these feelings are common.

7. Guidelines for section V:

Ask for specifics on any services the parent has received or is currently receiving.

If the parent is currently receiving services for himself/herself, inform him/her that because we are looking at the impact of this particular intervention on families we are asking that parents not receive any other psychotherapy services for themselves while the intervention is taking place. This is to ensure that any effects we observe are a result of our intervention and not other psychotherapy services. However, we will take their information and speak with the principle investigator for a case-by-case decision regarding their current services. Children can continue to receive behavioral and psychotherapy services.

8. Guidelines for section VI:

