2 = 4-5

3 = 6-7

4 = 8-9

5 = 10+

Strongly Agree=5 Agree=4 Not Sure=3 Disagree=2 Strongly Disagree=1

34. There are some things my child does that really bother me lot.

35. My child's behavior is more of a problem than I expected.

36. My child makes more demands on me than most children.

***Score the PSI on excel spreadsheet. If total stress score is at or above 85th percentile (raw score of 110 or higher) then proceed with phone screen. If parent has a score below the 85th percentile let parent know we are looking for parents who have high levels of parenting stress and, at this point in time, the parent does not meet that criteria.

V. Service Information-

Thank you for answering those. Just a few more questions. Are you currently receiving any psychological or behavioral services for yourself such as counseling, parent training class, or participating in a regular parent support group?

Yes No

If yes:

Type of service received:

Where: _____

When: _____

Ongoing? Yes No

By whom: _____

***If parent is receiving ongoing services inform him/her that *"Due to the nature of this intervention, if you are currently receiving psychological services I will review your specific case with the principal investigator and get back to you regarding your eligibility."*

Continue with phone screen and bring services to [name] attention.

VI. Exclusion Criteria Checklist

A. Is child able to walk unassisted? Yes No

B. Does child have issues seeing or hearing? Yes No

If yes...

• "Is your child blind? / Is your child deaf?"

• Extent of hearing / seeing issues: _____

***If child is blind or deaf, inform the parent, "Due to the nature of this intervention, we will not be recruiting children with significant vision or hearing difficulties at this time. The child will be asked to follow verbal directions and respond to certain visual patterns during the developmental evaluation. The presence of sight /

hearing issues would make this portion of our study difficult for your child."

***If child is non-ambulatory, note this but complete the phone screen. At the end of phone screen let parent know you need to bring this case to the research team and follow up with them in 1 week or less."

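### The protocol and the 2018 phone screen set different entry rules (more than 10 ECBI problems versus PSI-SF 110 or higher), and the change request does not withdraw the ECBI rule

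*Combined protocol and SAP*

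**What the plan says.** The protocol's Inclusion/Exclusion Criteria open with the target population: "All individuals invited to participate in the study will be parents of children with developmental delays and clinically significant behavior problems". Criterion 3 puts the behavioural part into practice: "parent(s) report more than 10 child behavior problems" on the ECBI. Criterion 4 requires that "the parent(s) is not receiving any form of psychological or behavioral treatment at the time of referral". No parenting-stress threshold appears among the criteria.

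The 2018 phone screen uses a different numerical rule. The scoring note in section IV of the form reads "If total stress score is at or above 85th percentile (raw score of 110 or higher) then proceed with phone screen", and the matching instructions say "If the parent does not reach the clinical cut off (score of 110), they will not be eligible for the study". For a parent already in treatment, the guidelines for section V provide a "case-by-case decision regarding their current services". The closing script in section VII of the form tells the family it is eligible.

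The IRB Change Request Form, in its summary of changes, says the team will "administer the Parenting Stress Index-Short Form 4th Edition instead of the Perceived Stress Scale during the phone screen". Item 3a, on removed exclusions or broadened inclusion, gives one entry: "The study will now focus on children with Autism Spectrum Disorder specifically, rather than children with developmental delays more broadly".

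**The concern.** The protocol's section on recruitment and screening makes the phone screen the step that decides eligibility before the first laboratory visit is booked. If that step does not apply criterion 3, the protocol's description of the sample is not enforced by anything a reader can find.

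This matters most for Aim 4, which asks whether children of treated parents show larger reductions in behaviour problems. The ECBI is one of the listed child outcomes at all three time points. The entry rule on it determines both whom the result describes and how much room for change the sample has on that measure. The PSI-SF is listed as a measure of parental stress, so it is not a substitute for a child conduct-problem count.

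**Working it through.** The plan gives no figure on this point to reproduce. The check compares the two rules and then asks whether they can disagree in practice.

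**1. The rules side by side**

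| Item | Protocol criteria | 2018 phone screen |
|---|---|---|
| Child behaviour | ECBI, more than 10 problems | No ECBI and no behaviour threshold |
| Parenting stress | No threshold | PSI-SF raw total 110 or higher |
| Parent in treatment | Not eligible | Case-by-case decision |
| Child's diagnosis | Developmental delay | Autism spectrum disorder (declared at item 3a) |

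Only the last difference is declared at item 3a. The switch to the PSI-SF is declared in the summary of changes, but as a replacement for the Perceived Stress Scale, not for the ECBI. Dropping a minimum problem count would broaden inclusion, which is what item 3a asks for, and it is not listed there.

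**2. Where the rules disagree, other criteria being met**

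- ECBI above 10, PSI-SF 110 or higher: both admit.
- ECBI above 10, PSI-SF below 110: the protocol admits, the screen rejects.
- ECBI 10 or fewer, PSI-SF 110 or higher: the protocol rejects, the screen admits.
- ECBI 10 or fewer, PSI-SF below 110: both reject.

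**3. Can a parent reach 110 with low ratings of child behaviour?** The printed PSI-SF has 36 items scored 1 to 5, so totals run from 36 to 180. The documents name the subscales but do not map items to them; the groupings below are a reading of the item wording. In each case the behaviour items are held at their minimum of 1.

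- Items 25 to 36 (12 items) at 1: maximum total 12 + 24 × 5 = 132. Reaching 110 needs a mean of (110 − 12)/24 = 4.08 on the other 24 items.
- Items 17, 21 and 24 also at 1 (15 items): maximum 15 + 21 × 5 = 120. Reaching 110 needs a mean of (110 − 15)/21 = 4.52 on the other 21.
- Items 18 to 20 (learning, smiling, ability) also at 1 (18 items): maximum 18 + 18 × 5 = 108, below the cut-off.
- The 12 parent-focused items (1 to 12) at 5 and all others at 1: 60 + 24 = 84, below the cut-off.

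A high-stress parent can therefore pass with the behaviour items at their minimum, but only with high scores elsewhere. These are extreme cases. A family with 10 or fewer ECBI problems need not score the behaviour items this low, so less extreme combinations also pass.

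**4. Could criterion 3 be applied later, before assignment?** The measures table lists the ECBI as a pre-treatment parent report. The questionnaire packet is due by the first visit, and families learn their group only after a baseline visit. The data could therefore be in hand in time. No available section says that the score is checked against the cut-off at that stage.

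**The case against.** The strongest reply is that two generations of the study are being read as one plan. The protocol text carries a 2011–12 timeline and spring and summer groups. The screen implements the later autism-only study with two active groups, following a grant proposal that is not available here. On that reading the screen is the operative rule and the criteria are simply out of date. Item 3a is also weak evidence of a complete list, since it asks about broadened criteria and was filled in with a narrowing. This stands in part: the documents do not settle whether the ECBI rule was meant to continue. But the protocol is still the governing text and nothing in the change request removes criterion 3, so the passages need reconciling under either reading.

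A second reply is that the ECBI may be checked at baseline. That is possible, but it is not written, and the screen's closing script already declares eligibility.

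Two stronger readings are tempting and are not supported. A reader might infer that the screen admits children without behaviour problems. Ten or fewer ECBI problems means not exceeding a conduct-problem cut-off, which is not an absence of problems. The PSI-SF also has a Difficult Child subscale and an item counting bothersome behaviours, so it partly selects for child difficulty. A reader might also infer a specific loss of power on Aim 4. The documents give neither the share of low-ECBI families among those passing the screen nor their expected effect. Selecting high-stress parents could also strengthen the mechanism under test, and Aim 4 draws on spouse and teacher reports as well.

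**Conclusion.** The contradiction is real and goes beyond missing detail: staff who follow the screen exactly can enrol families who fail criterion 3 and will reject some who meet it. The enrolled population may therefore differ from the one the protocol names. The conflict over parents already in treatment is a second, separate inconsistency of the same kind.

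The difference does not favour one arm, because both rules act before assignment. Low-ECBI entrants would have less room to improve on that scale, so some dilution of Aim 4 is plausible, but its size cannot be derived and no power figure should be attached to it.

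The conclusion assumes that the printed screening form, sections I to VIII, is complete, and that no page unavailable for review adds an ECBI check before assignment. It does not depend on which rule the sponsor intended. This should be corrected.

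**What to change.** Reconcile the protocol criteria, item 3a of the change request, the phone screen instructions and the screening form into one entry list. State which instrument, cut-off and time point decide entry.

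- If the ECBI rule stays, score it from the baseline packet and confirm it before the family is assigned. The closing script should then describe eligibility as provisional. The cost is that some families are found ineligible after a baseline visit.
- If the ECBI rule is dropped, declare this at item 3a and remove the claim of clinically significant problems from the population statement. The cost is wording only, but the result then describes a different population.

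In either case, compare the arms on Aim 4 with adjustment for baseline ECBI. The Data Analysis section offers dependent-sample t-tests as its example for child behaviour. Families selected for high scores tend to score lower on re-measurement without any treatment, and a within-group test would count that fall as benefit. A baseline-adjusted comparison between arms guards against this and uses data already collected.

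Reconcile criterion 4 with the case-by-case provision, and state who decides, on what basis, and that the decision comes before assignment. No new instrument or visit is needed for any of these changes.

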Sanders, J. L., & Morgan, S. B. (1997). Family stress and adjustment as perceived by parents of children with autism or down syndrome: Implications for intervention. *Child & Family Behavior Therapy*, 19(4), 15-32.

Singh, N. N., Lancioni, G. E., Winton, A. S. W., Fisher, B. C., Wahler, R. G., McAleavey, K., . . . (2006). Mindful parenting decreases aggression, noncompliance, and self-injury in children with autism. *Journal of Emotional and Behavioral Disorders*, 14(3), 169-177.

Singh, N. N., Lancioni, G. E., Winton, A. S. W., Singh, J., Singh, A. N., Adkins, A. D., & Wahler, R. G. (2010). Training in mindful caregiving transfers to parent-child interactions. *Journal of Child and Family Studies*, 19(2), 167-174.

Yirmiya, N., & Shaked, M. (2005). Psychiatric disorders in parents of children with autism: A meta-analysis. *Journal of Child Psychology and Psychiatry*, 46(1), 69-83.

Objectives

Aim 1: To determine whether MBSR is a feasible intervention with parents of children with developmental delays.

- Hypothesis: The majority of parents (minimum of 60%) who enter the program complete the full 8 weeks of the program. Although we hope for less attrition, this is a conservative estimate given that attrition from child psychotherapy in general is high, ranging from 40% to 60% (Wierzbicki & Pekarik, 1993).

Aim 2: To examine whether MBSR leads to reductions in parenting stress.

- Hypothesis: Parents will self-report significantly lower levels of stress post-intervention and at follow-up.

Aim 3: To investigate whether MBSR is associated with changes in parenting behavior.

- Hypothesis: Parent receiving the intervention will exhibit less negative and intrusive behavior and more positive and sensitive behavior compared to controls as evidenced in observational as well as self-report measures.

Aim 4: To determine whether reductions in parenting stress are associated with decreases in child behavior problems at post-intervention and at follow up.

- Hypothesis: Children of parents receiving MBSR will show greater reductions in behavior problems compared to children of waitlisted parents as evidenced by the participating parent, spouse/significant other, and teacher reports.

Aim 5: To evaluate whether parenting behavior mediates the relationship between parenting stress and child behavior problems.

- Hypothesis: Parenting behavior will mediate the relationship between parenting stress and child behavior problems such that, once parenting behavior is accounted for, the relationship between parenting stress and child behavior problems will be significantly reduced (partially mediated) or no longer significant (fully mediated).

Aim 6: To examine variables that may moderate the effect of the intervention (reducing parental stress) on child behavior problems.

- Hypothesis: The effect of the intervention in reducing parents' levels of stress and children's subsequent behavior problems will be greater for parents with less social support (e.g. marital adjustment, family support) and who have fewer psychological resources (e.g. low dispositional optimism, less feelings of self-mastery), are less satisfied with their parenting, and have a more negative relationship with their child pre-intervention. Additionally, parents of children with more difficult temperaments will also evidence greater intervention gains.

References

Wierzbicki, M., & Pekarik, G. (1993). A meta-analysis of psychotherapy dropout. *Professional Psychology: Research and Practice*, 24(2), 190-195

Procedures

Interested parents will either contact the MAPS project by phone, return a postcard requesting the PI to contact them, or submit their information on the MAPS website. If the family indicates interest in participation, the PI will conduct a phone screen (please refer to enclosed phone screen document). If the family meets eligibility for the study, an appointment will be scheduled for the initial laboratory assessment.

Prior to the initial laboratory assessment, parents will be mailed a packet of questionnaires that they will complete prior to coming into the lab. Only parents participating in the study will complete the packet; however, each parent's significant other (or if it is a single parent family another significant adult in the child's life) will complete two questionnaires (one about the child's behavior problems and about the child's social skills) in order to minimize shared method variance.

At the initial assessment, parents will be given an informed consent form that the PI or her staff will review with the parent (see informed consent procedures described above). After that, the parent and the child will participate in a 25-minute play assessment in the lab, which will be videotaped for later coding. Parent and child will be given a standardized set of toys and there

are 3 parts of the assessment: (1) *Child-led play* (parent is instructed to allow the child to choose any activity and play along with the child); (2) *Parent-led play* (parent is instructed to select an activity and to keep the child playing according to the parent's rules); and (3) *Clean-up* (parent is instructed to give the child a command to clean up). This task is standard procedure for the Dyadic Parent-Child Interaction Coding System (DPICS, Robinson & Eyberg, 1981), which will be used in this study to measure parenting behavior. After the observation task with the child, parents will meet with the experimenter to complete a demographic questionnaire and the Children's Global Assessment of Functioning Questionnaire. Parents will also be given a letter and two questionnaires for the child's teacher to complete. After completing these measures, the parents will draw a piece of paper out of a box which informs them whether they will be in the spring or summer intervention group.

Parents assigned to the spring group will begin intervention in March and parents assigned to the summer intervention will begin intervention in June. The intervention will follow the MBSR manual outlined by [name] (Kabat-Zinn et al., 1992). The intervention consists of three main components: (1) didactical material covering the concept of mindfulness, the psychology and physiology of stress and anxiety, and ways in which mindfulness can be implemented in everyday life to facilitate more adaptive responses to challenges and distress, (2) mindfulness exercises during the group meetings and as homework between sessions, and (3) discussion and sharing in pairs and in the larger group. The MBSR program includes eight weekly 2.5 hour sessions, a day-long meditation retreat after class 6, and daily home practice based on audio CDs with instruction. Formal mindfulness exercises include the body scan, sitting meditation with awareness of breath, and mindful movement. MBSR is an empirically supported secular (non-religious) based intervention that can be beneficial to all people. The PI has undergone formal training in MBSR through InsightLA (<http://www.insightla.org>) and has multiple collaborations with formal MBSR teachers. Currently, [name] is planning to deliver the intervention herself; however, if funding permits she will hire a certified MBSR teacher (who will complete HIPAA certification and obtain IRB approval before teaching).

After the completion of the project (all assessments have been conducted) parents will receive a short summary of their child's current and previous behavioral functioning in order to reinforce parents' efforts to improve their parenting skills as well as raise awareness of remaining concerns.

Robinson, E. A., & Eyberg, S. M. (1981). The dyadic parent-child interaction coding system: Standardization and validation. *Journal of Consulting and Clinical Psychology*, 49(2), 245-250.

Measures and Data Collection

See table below for information on measures and data collection time points (pre-intervention, post-intervention, and follow-up)

Measures for MAPS Program (Mindful Awareness & Parenting Stress)

Measure	Pre-Tx	Post-Tx	Follow-Up	Description	Type of Measure
Outcome Measures of Child Functioning					
Dyadic Parent-Child Interaction Coding System (DPICS)	X	X	X	Coding system that measures child behaviors that including whine, cry, yell, physical negative, smart talk, destructive, and noncompliance. These scores combine into a Total Child Deviance composite score.	Lab Observation
Child Behavior Checklist (Ages 1.5-5)	X	X	X	One of the most widely used measures of child behavior problems Each CBCL item indicates a child problem (e.g. fails to finish things he/she starts, temper tantrums or hot temper, sleeps more than most kids). For each item parent will indicate whether it is "not true" (0), "somewhat or sometimes true" (1), or "very true or often true" (2), now or within the past two months.	Parent Report
				This measure will be completed by participating parent as well as the spouse or other significant person nominated by spouse in order to minimize shared method variance.	
Caregiver-Teacher Report Form for Ages 1.5-5	X	X	X	Childcare provider/teacher version of CBCL	Teacher Report
Eyeberg Child Behavior Inventory	X	X	X	The Eyeberg Child Behavior Inventory (ECBI), designed to assess parental report of conduct behavioral problems in children and adolescents ages 2-16, measures the number of difficult behavior problems and the frequency with which they occur. Studies have indicated that the ECBI has good reliability and validity.	Parent Report
Social Skills Improvement System (SSIS)-Preschool Version, Parent Report	X	X	X	Child social skills will be measured using the SSIS. We believe that reductions in parenting stress may indirectly lead to improvements in children's social abilities. The SSIS is a widely used measure of social skills that asks parents to rate behaviorally specified social skills on two dimensions. The frequency dimension consists of a 3-point rating scale, including 0 (not true of the child), 1 (sometimes true), and 2 (often true). The second	Parent Report

Measure	Pre-Tx	Post-Tx	Follow-Up	Description	Type of Measure
Social Skills Improvement System (SSIS)-Preschool Version, Parent Report Continud	X	X	X	dimension, the importance of each skill, will not be assessed for this study. The scale yields scores that can be converted to standard scores ($M = 100$; $SD = 15$). The SSRS-P measures the domains of Communication, Cooperation, Assertion, Responsibility, Empathy, Engagement, Self-Control and yields a Total Social Skills score	Parent Report
Social Skills Improvement System (SSIS)-Preschool Version, Teacher Report	X	X	X	Teacher version of SSIS; also includes an Academic Competence Scale score that is not in parent version.	Teacher Report
Children's Global Assessment of Functioning (C-GAS)	X	X	X	The Children's Global Assessment Scale (CGAS) is a numeric scale (1 through 100) where parents rate the general functioning of children under the age of 18.	Parent Interview

Independent Variable Measures of Parental Stress and Overall Parental Functioning

Parenting Stress Index-Short Form	X	X	X	The PSI-SF (Abidin, 1995) is a 36-item questionnaire designed to measure the extent to which parents are experiencing stress. The PSI-SF contains subscales assessing stress in three domains on a 5-point scale: Parent-Child Dysfunctional Interaction (e.g. "My child rarely does things for me that make me feel good."), Difficult Child (e.g. "My child gets upset easily over the smallest thing"), and Parental Distress (e.g. "There are quite a few things that bother me about my life"). The sum of these three subscales creates a Total Parenting Stress score. The measure has high validity and good internal consistency (Reitman, Currier, & Stickle 2002).	Parent Report
Center for Epidemiological Studies- Depressed Mood Scale (CES-D)	X	X	X	In order to look at the impact of the MAPS Project on parental depression, parents will complete the CED-D, a 20-item self-report measure of depressive symptoms including mood, somatic complaints, and cognitions. Total scores can range from 0 to 60, with a cut-off of 16 for the clinical range. The CES-D has four subscales – somatic symptoms (7 items), depressed affect (7 items), positive affect (reverse scored; 4 items), and interpersonal functioning (2 items).	Parent Report

Measure	Pre-Tx	Post-Tx	Follow-Up	Description	Type of Measure
Symptom Checklist-35 (SCL-35)	X	X	X	A 35-item questionnaire completed by parents that measures perceived levels of distress and addresses psychological symptomatology across dimensions of anxiety, depression, hostility, and interpersonal relatedness.	Parent Report
Family Impact Questionnaire	X	X	X	50-item questionnaire designed to measure parents' perceptions of the impact of a child on the family relative to the impact that "most children his/her age have on their family".	Parent Report
Measures of Mediating Variables					
Dyadic Parent-Child Interaction Coding System (DPICS)	X	X	X	Coding system that measures parenting behavior including the following codes: Positive Parenting (DPICS-PP; includes praise, positive affect, and physical positive); Negative Parenting (DPICS-NP; includes negative commands, critical statements, and physical negative); and Total Commands (DPICS-TC; includes indirect and direct commands).	Lab Observation
Alabama Parenting Questionnaire-Parent Global Report	X	X	X	This questionnaire will be used to assess self-reported parenting practices. The APQ consists of 42 items presented with a 5-point endorsement scale (Never, Almost Never, Sometimes, Often, Always), which map onto five subscales (Poor Monitoring and Supervision, Inconsistent Discipline, Corporal Punishment, Positive Parenting Techniques, Parental Involvement), as well as the three broad factors structure (Positive Involvement, Negative/Ineffective Discipline, Deficient Monitoring). The APQ is a widely used self-report measure of parenting behavior.	Parent-Report
Parent Practices Interview	X	X	X	This questionnaire was adapted from the Oregon Social Learning Center's (OSLC) discipline questionnaire and revised for young children. The PPI can be administered as an interview or used as a self-report questionnaire completed by the child's primary caregiver. It has the following composites: Harsh Discipline, Harsh for Age, Inconsistent Discipline, Appropriate Discipline, Positive Parenting, Clear Expectations, and Monitoring.	Parent-Report

Measure	Pre-Tx	Post-Tx	Follow-Up	Description	Type of Measure
CCNES: Coping with Children's Negative Emotions Scale	X	X	X	A 72-item questionnaire measuring the degree to which parents perceive themselves as reactive to young children's negative affect in distressful situations. Six subscales are derived that reflect the specific types of coping responses parents tend to use in these situations (distress reactions, punitive reactions, expressive encouragement, emotion-focused reactions, problem-focused reactions, and minimization reactions).	Parent-Report
Measures of Moderating Variables					
Dyadic Adjustment Scale (DAS)	X	X	X	32-item self-report measure of marital adjustment. It has 4 subscales: Dyadic Consensus, Dyadic Satisfaction, Affectional Expression, and Dyadic Cohesion	Parent-Report
LOT-R: Life Orientation Test-Revised	X	X	X	The Life Orientation Test-Revised (LOT-R) assesses individual differences in generalized optimism versus pessimism. This measure has been used in a good deal of research on the behavioral, affective, and health consequences of this personality variable.	Parent-Report
Life Experiences Survey	X	X	X	49-item questionnaire regarding major events that have occurred within the past 6 months and the perceived degree of impact (or stress) related to these individual events.	Parent-Report
Family Relationship Index of the Family Environment Scale	X	X	X	The Family Relationship Index of the Family Environment Scale has three subscales that measure family Cohesion (the degree of commitment and support family members provide for one another), Expressiveness (the extent to family members are encouraged to express their feelings directly), and the Conflict (amount of openly expressed anger and conflict among family members).	Parent-Report
General Life Satisfaction Index	X	X	X	A 1-item measure asking parents to rate their satisfaction with their current life situation.	Parent-Report

Measure	Pre-Tx	Post-Tx	Follow-Up	Description	Type of Measure
Family Support Scale	X	X	X	The self-report Family Support Scale (FSS) measures parents' satisfaction with the support they receive in raising a young child. The scale consists of 18 items covering such sources of support as the immediate family, relatives, friends and others in the family's social network, social organizations, and specialized and generic professional services. In addition, the scale provides 2 open-ended items for parents to assess other sources of support not included in the 18 items. The parent rates each source of support on a 5-point Likert scale (ranging from not at all helpful (1) to extremely helpful (5)).	Parent-Report
Self-Mastery Scale	X	X	X	A 7-item questionnaire completed by parents measuring perceived level of control over life events.	Parent-Report
Child Behavior Questionnaire	X			The Children's Behavior Questionnaire has been designed to measure temperament in children. The CBQ assesses fifteen dimensions of temperament.	Parent Report
Parenting Relationship Questionnaire	X	X	X	47-item questionnaire designed to capture a parent's perspective of the parent-child relationship. Subscales: Attachment, Discipline Practices, Involvement, Parenting Confidence, and Relational Frustration.	Parent-Report
